Title: Enhancing Child Digital Dietary Self-monitoring: Proof-of-concept Trial

NCT Number: NCT06193967

Document Date: 11/07/2024

For this proof of concept trial, a mobile-optimized, web-based dDSM log will be developed to test the two positive reinforcement strategies: caregiver praise and gamification. The dDSM log will be developed as a mobile-optimized website, rather than an app, so that phone operating system will not be a limitation of use. Families will therefore be able to access the dDSM log from a computer, smartphone, or other internet-enabled device. All dDSM logs will include three basic features: 1) ability to log targeted food groups with amounts and serving consumed, 2) ability to indicate logging is complete for the day, and 3) access to a help feature that provides guidance on tracking and serving sizes. Children will be instructed to self-monitor their daily intake of the following food groups: fruits, vegetables, sweet and salty snack foods, and sugar-sweetened beverages (SSBs). DSM will focus on these four food groups because they have an established influence on health. Fruit and vegetable consumption is associated with decreased risk of chronic disease, and reduced consumption of energy-dense foods like sweet and salty snacks and SSBs is recommended for weight loss in children. Additionally, these food groups are frequently targeted in childhood obesity treatment and are easily understood by young children.

Using a 2x2 factorial design, each child-caregiver dyad will be randomly assigned to 1 of 4 conditions: BASIC, PRAISE, GAME, or PRAISE+GAME. Each child will be provided a unique URL to access a personal dDSM log with the appropriate, randomly assigned features (praise and/or gamification). Caregivers will be provided a separate unique URL to review their child's log and access the caregiver check-in feature, which will not be available in the child link. For PRAISE and PRAISE+GAME conditions, caregivers will be instructed to provide daily process praise to their child related to DSM behaviors (see additional description in the Family dDSM Training section below). While DSM is frequently implemented within treatment, children in the proposed study will engage in DSM without a concurrent intervention to tightly control the influence of the independent variables on DSM behaviors only (as compared to having all adult caregivers learning how to praise or having caregivers focus their praise on achieving dietary goals, which are both standard components of family-based, childhood obesity interventions). Thus, only caregivers randomized to PRAISE or PRAISE+GAME will be instructed on praise and, in the absence of dietary goals for intervention, caregivers will only have one behavior (DSM) to praise. For GAME and PRAISE+GAME conditions, logs will integrate three game mechanics: points, levels, and a virtual pet. Points will be accumulated for engaging in DSM behaviors, and accrual of points will evolve a virtual pet over time, acting as digital token economy. The number of points to level up will increase with each level, so that each consecutive level is harder to attain than the previous one. At the end of the 4-week DSM period, families who complete follow-up assessments will receive two \$25 gift cards (one for caregiver, one for child) and will be provided access to a short online behavioral nutrition education program.

The primary DSM outcomes will be frequency (i.e., number of days any food/beverage item is tracked or logging is marked complete) and timing (i.e., how many sessions of recording are completed each day and whether foods/beverages were logged on the day of intake). On days in which no targeted food group is consumed, children will have the ability to mark logging as complete for the day (Figure 1a). Indicating logging is complete in the absence of any tracked foods will be considered a "tracked" day. Pre-post changes in intrinsic motivation will also be examined.

Study Population and Recruitment

For the proof-of-concept trial, children ages 8-12 years at or above a healthy weight [defined as body mass index (BMI)-for-age \geq 5th percentile] who report eating foods/beverages (any serving size) from ≥ 2 targeted food groups (fruits, vegetables, sweet and salty snack foods, and SSBs) on ≥ 3 days/week each and who have an adult caregiver ≥ 18 years of age willing to participate will be eligible for enrollment. Families will be excluded if the child is already self-monitoring his or her diet or has major psychiatric diseases or organic brain syndromes, or if the family does not live in the greater Knoxville area or does not speak English. Additionally, families must have reliable access to the internet via phone, computer, or another device that the child is able and permitted to operate.

Potential participants will be identified via several strategies. First, researchers will utilize the ongoing recruitment efforts for the Families Becoming Healthy Together (FBHT) trial (NIH 1R01DK121360; PI: [name]) being conducted at the Healthy Eating and Activity Laboratory at the University of Tennessee. FBHT is an intensive 18-month childhood overweight and obesity treatment program enrolling a similar population (i.e., children 8-12 years). Given the length and intensity of the FBHT intervention, it is not a good fit for all families, and/or families might not meet the stringent inclusion and exclusion criteria. Families who screen ineligible for FBHT will be asked whether they would like to receive information about the proposed study. If yes, families will be referred to research staff of the proposed study who will provide a description of the study and complete eligibility screening by phone. Other recruitment strategies include recruitment flyers that will be distributed to UT departments via campus mail, provided to the daycare centers and other businesses/organizations (e.g., YMCA) for distribution to parents, distributed at community events (e.g., farmers markets), and posted in public spaces in the Knoxville area, and online advertisements will be posted on social media (e.g., Facebook) that provide a link to a Qualtrics form that collects contact information and obtains permission to contact. Additionally, researchers will set up a booth at the Cherokee Mills office campus where the University of Tennessee operates an office space. This campus is also occupied by a Cherokee Health Systems clinic that serves both adults and children who may be eligible for the proposed study. Finally, ResearchMatch will be used to contact a de-identified group of potential volunteers that might be interested.

Study Flow

After an initial phone screening to determine eligibility, interested families will be invited to attend an orientation at the Healthy Eating and Activity Laboratory (HEAL) at the University of Tennessee Knoxville. For families who agree to participate, caregivers will complete informed consent forms and children will provide assent. After consent/assent, families will complete baseline assessment measures (see Measures). Immediately after baseline measures are completed, families will be told their assigned condition (randomized using a random numbers table). All families will be provided information on the benefits of DSM and the relationships of the four targeted food groups with child health. Families will be informed that the child's DSM records over the next 4 weeks will be used to provide individualized feedback on their child's nutrition status at their follow-up visit, at which time they will receive access to a short online behavioral nutrition education program (described below).

Each family will be provided a access to a dDSM log that matches group assignment. Caregivers will be instructed to review their child's DSM each day and complete a caregiver check in. Additionally, to get children started, all caregivers will be instructed to sit with their child each day for the first 3 days of the DSM period to help their child log any foods consumed

from targeted food groups. If no logging is completed within the first 4 days of a family's DSM period, a research assistant will reach out to the caregiver to problem solve and provide support.

At the end of the 4-week DSM period, families will schedule a virtual appointment to complete follow-up assessment measures. To provide feedback to families, days for which tracking was marked as completed in the dDSM log will be entered into the Nutrition Data System for Research (NDSR) software to determine servings of fruits and vegetables consumed, as well as intake of added sugars and saturated fats from sugar-sweetened beverages and sweet and salty snack foods. These values will be entered into a feedback template that compares the child's intake to the recommendations in the Dietary Guidelines for Americans (DGA) 2020-2025. Families will also be provided access to a short online behavioral nutrition education program that will consist of four modules: 1) DGA recommendations and basic nutrition information, 2) establishing a healthy home environment, 3) positive reinforcement of healthy behaviors, and 4) pre-planning and problem solving.

Family dDSM Training. After baseline measures, families will complete a DSM practice session using their dDSM log under the observation of research staff. The family's personal dDSM will be used; therefore, GAME/PRAISE features related to the family's assigned condition will be included. The family will practice logging foods and beverages from a standard list and will then be instructed to mark logging as complete for the day. Research staff will answer any questions the family has and will explain how to use the "Help Me Log" feature. Caregivers will also be shown how to complete the caregiver check in feature.

For families randomized to the PRAISE conditions (PRAISE and PRAISE+GAME), caregivers will also provide praise to their child during the DSM practice session so that research staff can observe and provide feedback. During training session, caregivers will be provided a brief training on providing process praise. A description of process praise will be provided, including a list of examples, and caregivers will complete a brief "quiz" in which they attempt to correctly identify process praise statements. Caregivers will also be encouraged to avoid negative reinforcement (e.g., nagging). If the caregiver notices the child is not using the dDSM log, he or she will be encouraged to engage in problem solving/preplanning (rather than nagging) to encourage the child to self-monitor. If the caregiver notices the child is engaging in undesirable behaviors (e.g., recording unhealthy foods), this should be ignored rather than criticized. Additionally, caregivers will be encouraged to provide the praise as close to the occurrence of the behavior as possible to increase its effectiveness. For PRAISE conditions, completion of the caregiver check-in will prompt the caregiver to also complete a praise check-in ("Would you also like to complete a praise check in?"). If no praise check-ins are completed within the first 4 days of the DSM period, a research assistant will reach out to the caregiver to problem solve and provide support.

For families randomized to GAME conditions (GAME and PRAISE+GAME), children and caregivers will observe how points are accrued during the DSM practice session. Prior to the practice session, research staff will explain how points are earned and how points help to "level up" the virtual pet. Points will be accrued and represented in the dDSM log in real time so that children will immediately be rewarded for engaging in DSM behaviors.

At the conclusion of the study, results will be disseminated to former participants via email.

Sample Size

Targeted enrollment will be 40 families (10 families per group) for the proof-of-concept trial.

Measures

Sample characteristics

Demographics. Demographic information will be used to describe the study sample. Information collected will include child and caregiver age, race and ethnicity, and gender and caregiver marital status, education level, employment status, and household income.

Child height and weight. Child height and weight will be collected to confirm study eligibility, and BMI z-score will be calculated based on sex and age.

Parenting style. Previous research has associated parenting style with intrinsic motivation in children. To determine parenting style, caregivers will complete Parenting Styles and Dimensions Questionnaire (PSDQ)-Short Version. The PDSQ-Short Version is a 32-item questionnaire that uses a 5-point Likert scale (never to always) to provide scores for three parenting style factors: authoritativeness, authoritarianism, and permissiveness.

Primary measures: DSM behaviors

Foods, beverages, and serving sizes entered in the dDSM logs by participants will automatically populate a web-based spreadsheet that will collect participant ID number, date and time of entry, food/beverage name, and serving size. This spreadsheet will be exported to Microsoft Excel, and data management and analysis will be conducted in SAS Enterprise Guide 8.3.

Frequency. I.e., number of days with any logging. DSM frequency has been shown to predict success in family-based based childhood overweight and obesity programs. A day will be counted as “tracked” if any food or beverage is logged on that day or, if no food or beverage is logged, the “Logging Complete” button is clicked.

Timing. I.e., proportion of days on which food/beverage items were tracked on the day of intake, as well as the average number of logging sessions per day. Sessions will be considered as distinct tracking events if they occur >15 minutes apart.

Secondary measures

Child intrinsic motivation. Gamification and caregiver praise may differentially affect child motivation to engage in DSM. The Task Evaluation Questionnaire of the Intrinsic Motivation Inventory (IMI) will be used to determine whether are differences in pre-post changes in child intrinsic motivation. This questionnaire consists of 22 items and utilizes a 5-point Likert scale (not at all true to very true) to assess interest/enjoyment, perceived choice, perceived competence, and pressure/tension. At baseline, the measure will be administered after the child has practiced using dDSM with the research assistant so that he or she has some familiarity with the behavior before completing the measure.

Child motivation to change eating behaviors. Child’s motivation to change eating habits will be measured, as this may influence engagement in DSM. Children will be asked to complete the

8-item diet subscale of the Motivation to Exercise and Diet Questionnaire—Adapted for Children (MED-C), which is based on self-determination theory. The MED-C diet subscale utilizes a 5-point Likert scale (never to always) and includes 5 items related to motivation and 3 items related to self-determination theory needs (autonomy, competence, relatedness). This validity of the questionnaire has been tested in children aged 7 to 11 years.

Child dietary intake. The act of self-monitoring a behavior may result in reactivity, or improvements in the monitored behavior in the absence of other intervention. Thus, child dietary intake will also be assessed at baseline and follow-up using the Block Food Screener for Ages 2-17 2007. The instrument asks about intake in the “last week” and focuses on take of fruit, fruit juices, vegetables, potatoes (including French fries), whole grains, animal-based proteins, dairy, legumes, saturated fat, added sugars (in sweetened cereals, SSBs), glycemic load and glycemic index. It takes approximately 10-12 minutes to complete.

Usability and acceptability

Child/Caregiver usability and acceptability survey. A survey will be developed (adapted from Marsac et al.108) to capture family's experiences with the dDSM log, as well as the caregiver praise (PRAISE and PRAISE+GAME only) and gamification (GAME and PRAISE+GAME only) features. The survey will address both usability and acceptability.

Adherence and dose

Caregiver praise. To examine whether the caregiver praise manipulation was successfully implemented, the number of completed caregiver check-ins in which the caregiver marked ‘yes’ for praise provided will be calculated.

Caregiver reminder questionnaires. To examine whether caregivers avoided the use of negative reinforcement (e.g., nagging), items related to caregiver reminders will be administered to the child and parent at follow up.

Gamification. To examine whether the gamification manipulation was successfully implemented, the average number of points received/levels achieved will be calculated. Higher point totals and maximum levels will indicate receipt of a higher dose of the gamification manipulation.

Statistical Analysis

Summary statistics will be used to describe sample characteristics (demographics, child weight status, parenting style). Intent-to-treat analysis will be performed, and missing data will be addressed using a multiple imputation approach. Absence/presence of DSM will be coded as ‘0’ or ‘1’ for each day, with ‘0’ representing no food or beverage tracked AND tracking not marked as complete for the day and ‘1’ representing ≥ 1 food or beverage tracked AND/OR tracking marked as complete for the day. Therefore, the possible range for overall DSM frequency for the 4-week period will range from 0 (no DSM any day) to 28 (DSM on all days). The possible range for DSM by week will range from 0 to 7. DSM timing will be calculated two ways: 1) the mean number of DSM sessions per day (must be >15 minutes apart to be considered distinct sessions) and 2) the percent of food or beverage items tracked on the day of intake (i.e., the number of food or beverage items tracked on the day of intake divided by the total number of food or beverage items tracked). To assess dose of positive reinforcement

received, the mean number of points accumulated by children in the GAME groups will be calculated, as well as the total number of days in which praise check-ins were completed for children in the PRAISE groups.

To determine the main effects of positive reinforcement on DSM behavior, a 2x2 factorial ANOVA will be conducted with gamification and caregiver praise status as the independent variables and a dependent variable of DSM behavior (frequency or timing). A gamification*caregiver praise interaction term will also be included in the model to test for interactive effects.

To examine how DSM changes over time, linear mixed-factor ANOVA will be used with a between-subject factor of group, a within-subject factor of time (week), and a dependent variable of DSM behavior (frequency or timing). Additionally, graphical representations of daily DSM frequency and timing by group will be plotted to help visualize trends over time.

To explore how positive reinforcement influences motivation, a 2x2 factorial ANCOVA will be conducted with gamification and caregiver praise status as the independent variables, a dependent variable of intrinsic motivation at follow-up, and a covariate of intrinsic motivation at baseline. A gamification*caregiver praise interaction term will also be included in the model to test for interactive effects. This statistical procedure will be repeated with the other secondary measures of child motivation to change eating behaviors and child dietary intake, with follow-up measures as the dependent variable and baseline measures as covariate.

To examine how changes in secondary measures over time, linear mixed-factor ANOVA will be used with a between-subject factor of group, a within-subject factor of time (baseline and follow-up), and a dependent variable of intrinsic motivation, child motivation to change eating behaviors, or child dietary intake, respectively.

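### The week effect mixes the end of caregiver start-up help on days 1-3 with change in the child's own logging, and no planned test separates the two (minor)

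*Combined protocol and SAP*

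**What the plan says.** Study Flow gives the start-up instruction to every arm: "all caregivers will be instructed to sit with their child each day for the first 3 days of the DSM period". Other caregiver contact continues after that. Caregivers are asked to review the child's "DSM each day and complete a caregiver check in", and staff contact the caregiver under the condition "If no logging is completed within the first 4 days".

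The Statistical Analysis section codes each day 0 or 1. Overall frequency runs from 0 to 28, and for the weekly score "The possible range for DSM by week will range from 0 to 7". No day is left out of either range. The test of change is then defined: "To examine how DSM changes over time, linear mixed-factor ANOVA will be used with a between-subject factor of group", with week as the within-subject factor and frequency or timing as the outcome. Daily plots by group are also planned, as a visual aid.

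The plan contains no indicator for the assisted days, no stated contrast among weeks 2-4, and no companion analysis without days 1-3.

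**The concern.** The behaviour of interest is the child's own monitoring: "Children will be instructed to self-monitor their daily intake of the following food groups". The mixed-factor ANOVA is the only planned test of how that behaviour changes over the four weeks. Its week factor compares one week in which three days carry instructed sit-down help with three weeks in which none do. Time has no control group here, because all arms receive the same instruction on the same days.

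Two misreadings are possible. A fall from week 1 could be reported as waning engagement when logging without sit-down help was flat. Or a rise in logging without sit-down help could be masked in any comparison with week 1.

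**Working it through.** **Inputs from the documents.** Assisted days: 1-3, all arms (Study Flow). Weekly score 0-7 and total 0-28 (Statistical Analysis). 10 families in each of 4 groups (Sample Size). The plan gives no figure of its own to reproduce on this point.

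**Share of assisted days.** Week 1: 3/7 = 43%. Weeks 2-4: 0. Whole period: 3/28 = 11%.

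**Expected shift.** Let q be the daily logging rate on days 1-3 and p the rate on all other days. Week 1 has mean 3q + 4p and each later week 7p, so the excess is (3q + 4p) - 7p = 3(q - p).

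**Chance that the planned week F-test is significant at 5%.** All rates are assumed. The simulation has 40 children, a child random effect with SD 1 logit, a constant rate on days 4-28, and a latent lag-1 correlation between days of 0, 0.4 or 0.8.

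| p, q | Excess, days | Rejection at correlation 0 / 0.4 / 0.8 |
|---|---|---|
| 0.6, 0.95 | 3 × 0.35 = 1.05 | 99 / 95 / 75% |
| 0.6, 0.95, half of families helping | 0.53 | 48 / 32 / 21% |
| 0.6, 0.8 | 3 × 0.20 = 0.60 | 63 / 43 / 25% |
| 0.8, 0.95 | 3 × 0.15 = 0.45 | 56 / 39 / 22% |
| 0.8, 0.95, half of families helping | 0.23 | 15 / 12 / 9% |
| 0.9, 0.95 | 3 × 0.05 = 0.15 | 13 / 10 / 7% |
| q = p | 0 | 5 / 5 / 6% |

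In the same scenarios a weeks 2-4 F-test and a linear daily slope over days 4-28 each reject in 4-6%. So does the group-by-week test when the arms are equal.

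**Masked rise (assumed rates).** Take 95% on assisted days, and 60, 63.3, 66.7 and 70% on other days in weeks 1-4. Week 1 is 3 × 0.95 + 4 × 0.60 = 5.25. Weeks 2-4 are 7 × 0.633 = 4.43, 7 × 0.667 = 4.67 and 7 × 0.70 = 4.90. Week 4 falls below week 1 although logging without sit-down help rose by 10 points. The rise from week 2 to week 4 remains visible.

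**What a companion slope costs in power.** The test is a per-child linear slope with no help effect. At p=0.6, q=0.95 a days 1-3 indicator gave the same rejection as dropping those days (5.2% each).

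| True pattern (correlation 0) | Slope, days 4-28 | Slope, days 1-28, no indicator |
|---|---|---|
| Weekly steps, 70% to 60% | 65% | 76% |
| Daily linear decline, 70% to 60% | 47% | 60% |

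At correlation 0.8 the days 4-28 slope has 23-25% and 17%. For early fading from 85% toward 60%, at correlation 0, it has 42% with a 4-day time constant and 8% with a 2-day one. The planned week F-test has 95% and 65% for those two paths.

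**The case against.** The strongest reply is that the plan promises only to examine how logging changes over time and never says that the week effect measures unaided engagement. That is correct. A reader might take the 99% in the table for a false-positive rate. It is not: recorded logging does fall when help ends, and the test detects a true change in the outcome as defined. What stands is that the test cannot say why it fell.

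A reader might also infer that the praise and gamification comparisons are biased. The documents do not support this, because the help instruction is the same in every arm. It could narrow arm differences on 3 of 28 days. The group-by-week pattern could be distorted only if help works differently between arms.

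The daily plots may show a step after day 3, and the weekly scores allow a look at weeks 2-4. Both help, but the plots give no estimate or test, and no weeks 2-4 contrast is stated.

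The most important counter-argument limits the remedy. Days 1-3 are both the helped days and the earliest days, in every arm, so no analysis of these data can fully separate help from early fading. It would be tempting to accept fading only if it persists without days 1-3. That rule fails. Under true early fading with no help effect, the planned test is significant and the test using days 4-7 for week 1 is not in 50-55% of trials at correlation 0, and in 19-31% at 0.8.

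**Conclusion.** The concern holds in a limited form, and its severity is minor. The pooled week effect and any contrast with week 1 contain a component of 3(q-p) days that comes from start-up help. Its size cannot be obtained from the documents, which give no logging rates and describe no measure of whether caregivers sat with the child. The figures rest on assumed rates, uptake and correlation, and run from negligible to large. For timing, the size cannot be computed at all. Only the interpretation of the time analysis is affected. The 28-day 2x2 comparison, contrasts among weeks 2-4, and the group-by-week test under equal help are not biased.

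**What to change.** Keep the by-week ANOVA and the 0-28 total as planned, and prespecify one companion time analysis:

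- **Model.** A daily model over days 1-28 with a days 1-3 indicator and a linear day trend, allowing for correlation between days within a child. Report the trend over days 4-28 with its confidence interval, for frequency and, where it can be defined by day, timing.
- **Reporting.** State that week 1 includes three days of instructed sit-down help, and that a drop confined to days 1-3 cannot be attributed to either the end of help or early fading.
- **Reading.** A trend in the companion analysis supports change beyond start-up help. Its absence must not be read as no fading.
- **Wording.** Describe days 4-28 as being without instructed sit-down help, not as unassisted, because caregiver review continues and staff may contact families who have not logged.

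No separate days 4-28 count is needed, since the comparison it would check is not biased. The cost is SAP wording and one added analysis. The log spreadsheet already "will collect participant ID number, date and time of entry, food/beverage name, and serving size", so no new data, visits or changes to caregiver instructions are required. The downside is lower power, and no ability to detect fading confined to days 1-3. That is why the companion analysis accompanies the planned one and does not replace it.

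### PRAISE caregivers are told to ignore the recording of unhealthy foods, although recording snacks and sugary drinks is part of the one behaviour they are meant to praise

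*Combined protocol and SAP*

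**What the plan says.** The opening design description of the combined protocol and SAP asks children to "self-monitor their daily intake of the following food groups: fruits, vegetables, sweet and salty snack foods, and sugar-sweetened beverages". It explains the choice of groups partly by noting that "reduced consumption of energy-dense foods like sweet and salty snacks and SSBs is recommended for weight loss in children", so snacks and sugar-sweetened beverages (SSBs) are the groups a caregiver would naturally take to be unhealthy.

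The same opening text defines the praise manipulation. In the two praise arms, "caregivers will be instructed to provide daily process praise to their child related to DSM behaviors". Families receive no concurrent dietary treatment, and the stated reason is control of the independent variables: "in the absence of dietary goals for intervention, caregivers will only have one behavior (DSM) to praise". Praise training is confined to those arms: "only caregivers randomized to PRAISE or PRAISE+GAME will be instructed on praise".

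Family dDSM Training, in the paragraph on the PRAISE conditions, then says: "If the caregiver notices the child is engaging in undesirable behaviors (e.g., recording unhealthy foods), this should be ignored rather than criticized". The following sentence encourages caregivers to give praise promptly after the behaviour it rewards.

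**The concern.** Recording a food and eating it are different acts. The design makes recording the target, whatever the food. The training sentence attaches the word undesirable to the recording, so an accurate entry for a snack or SSB falls under two instructions at once.

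What is at stake is what the praise factor means. The trial sets out to test praise for self-monitoring (DSM), kept apart from praise for dietary goals. If caregivers praise fruit and vegetable entries and pass over snack and SSB entries, the delivered manipulation is a mixture of the two. Because this training is given only in the praise arms, any effect falls on the praise main effect and on the praise-by-gamification interaction. In PRAISE+GAME, one snack entry could earn points, since no distinction by food type is stated for points, and yet be ignored by the caregiver. A weak praise result would then be hard to attribute either to praise itself or to the instruction.

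**Working it through.** **Step 1: the texts side by side.**

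| Point | Opening design description | Family dDSM Training |
|---|---|---|
| Recording a fruit or vegetable | DSM, to be praised | No exception made |
| Recording a snack or SSB | DSM, to be praised | An example of undesirable behaviour, to be ignored |
| Eating a snack or SSB | No dietary goal, so not a target of praise | Not mentioned in this sentence |

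No other section resolves the conflict in the second row. The training script, example list and quiz are not in the documents, so it cannot be known whether they draw the distinction.

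**Step 2: the plan's own figures.** Sample Size gives 10 families in each of 4 groups: 4 × 10 = 40. The praise arms hold 2 × 10 = 20 families, so the praise main effect compares 20 with 20. The affected food groups are 2 of 4. That is a count of categories; the documents do not give the share of entries. They also state no alpha, power, effect size or SD.

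**Step 3: which outcomes are exposed.**
- Frequency (Primary measures; Statistical Analysis) is scored 0 or 1 per day. One entry of any kind, or marking the log complete, makes a tracked day. Losing some snack entries changes it only on days with no other logging.
- Timing is scored on sessions per day and, in Statistical Analysis, on the percentage of items logged on the day of intake. Each entry or session carries weight, so these measures are more exposed. The direction is not fixed for the percentage: a snack logged late lowers it, while a snack never logged leaves both numerator and denominator.
- The adherence check (Adherence and dose) counts check-ins marked yes for praise. It does not record what was praised or ignored.

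**Step 4: how often a day might hold nothing but snack or SSB entries (illustration).** Assume k independent entries on a logged day, each a snack or SSB with probability s. The share of such days is s^k.

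| s | k = 1 | k = 2 | k = 3 | k = 4 |
|---|---|---|---|---|
| 0.50 | 50% | 25% | 12.5% | 6% |
| 0.75 | 75% | 56% | 42% | 32% |
| 1.00 | 100% | 100% | 100% | 100% |

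The last row is the extreme case. Study Population and Recruitment admits a child who qualifies on any two of the groups, so one who qualifies on snacks and SSBs alone is eligible. How common this is, the documents do not say.

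**Step 5: what dilution would do to power (illustration).** Assume two-sided alpha 0.05 and the normal approximation with 20 against 20. The standardised difference detectable with 80% power is (1.960 + 0.842) × √(2/20) = 0.89 (0.91 using t with 36 df). With an assumed true effect d = 0.8, reduced by a fraction L, power is approximately Φ(0.8(1 − L)√10 − 1.960):

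| L | Diluted d | Power |
|---|---|---|
| 0 | 0.80 | 72% |
| 0.06 | 0.752 | 66% |
| 0.25 | 0.60 | 48% |
| 0.50 | 0.40 | 24% |

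The values of L match the s = 0.50 row of Step 4 at k = 4, 2 and 1. Using them this way assumes that caregivers follow the sentence literally and that the effect shrinks in proportion to the share of such days. Neither is established.

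**The case against.** The strongest reply is that the sentence contrasts ignoring with criticising. It follows advice against nagging, and its evident purpose is to prevent criticism. It does not tell caregivers to withhold praise, and the requirement of daily process praise carries no exception by food type. On a day of snack entries only, a caregiver can still praise prompt logging, repeated sessions or marking the log complete. Staff also observe the caregiver's praise during the practice session, and every caregiver sits with the child for the first 3 days, which may correct a misreading. This stands, and it limits the likely size of the effect. It does not remove the conflict, because the act named as undesirable is still recording.

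A reader might infer that half of the child's self-monitoring goes unpraised. The documents support only 2 of 4 food groups, not half of the entries, days or praise occasions.

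A reader might also infer that the praise comparison is biased, or that its effect is pushed below zero. The documents do not show this. Randomisation still gives a valid comparison of the praise package as delivered; the doubt concerns what that package represents.

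Nor would selective logging necessarily be confined to the praise arms. All families are taught how the four groups relate to health and know that the log feeds their nutrition feedback. The log stores food names, so snack and SSB entries can be compared by arm, and dietary intake as an outcome comes from a separate screener. These points make a null praise result less opaque than it might seem, although none of them shows what caregivers praised.

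**Conclusion.** The contradiction is real and lies in the plain text of one of the two experimental factors. It concerns 2 of the 4 food groups and the 20 families in the praise arms. Read literally, it makes praise partly dependent on food type and could attenuate the praise contrast, with timing more exposed than frequency and no adherence measure able to detect it.

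The size is not fixed by the documents. Under the assumptions in the working, power at d = 0.8 runs from 72% with no dilution to 24% with half the effect lost. That range shows how little margin 20 against 20 leaves; it is not an estimate of the loss. The point is one of construct validity with possible attenuation, and its severity is moderate.

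**What to change.** Before training is delivered, reconcile Family dDSM Training with the opening design description:

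- Remove the recording of unhealthy foods as the example of undesirable behaviour.
- Make the training text, the list of praise examples and the quiz separate two things: recording a food from any of the four groups, which is the DSM behaviour to praise, and the food choice itself, which is not a target of praise or criticism.
- Keep the instruction not to criticise.

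Optionally, the praise check-in could record what was praised, which would let adherence to the intended manipulation be described.

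The core change is to wording only. It needs no extra visits or staff, and no change to the sample size, outcome definitions or analysis. The optional item would add one field to an existing check-in.
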